## 4.0 PARTICIPANT SELECTION

### 4.1 Inclusion Criteria

Patients must meet all of the following inclusion criteria to be enrolled into the study:

1. Willing and able to sign informed consent and comply with the protocol, including clinic visits to receive weekly vesigenurtacel-L injections for 12 doses followed by either monthly vesigenurtacel-L injections for three months in Phase 1 or three courses of three once-weekly injections in Phase 2.
2. Histologically or cytologically confirmed non-muscle invasive bladder cancer [Ta, T1 or Tis (CIS)]. Papillary disease must have been removed by transurethral resection or fulguration.
3. Either
  - i. High-risk disease, defined as T1 and/or high-grade and/or CIS, *or*
  - ii. Intermediate-risk disease defined as Ta low-grade with at least three of the following four risk factors: multiple tumors, tumor size > 3cm, early recurrence (<1 year from previous staging procedure), or recurrence with a frequency of more than once in any 12 month period.
4. Patients must be BCG naive or have completed previous BCG treatment >12 months prior to the baseline staging procedure.
5. For Phase 2 only: Arms 1, 2, and 3: Suitable, in the opinion of the investigator, to receive a 6-week course of induction intravesical BCG in the adjuvant setting within 6 weeks following the baseline staging procedure for the current occurrence of non-muscle invasive bladder cancer. Arm 4: Suitable for monotherapy vaccine administration post-TURBT. For Phase 1 only: Has previously received 3-6 weekly doses of BCG.
6. Age  $\geq$ 18 years
7. Lab parameters:

- Albumin  $\geq 2.5$  mg/dL
  - Total bilirubin  $< 1.5$  mg/dL
  - Alanine transaminase (ALT) and aspartate transaminase (AST)  $\leq 2.5 \times$  upper limit of normal (ULN)
  - Serum creatinine  $\leq 2.2$  mg/dL or calculated creatinine clearance  $> 35$  mL/minute per the Cockcroft-Gault formula
  - White blood cell (WBC) count  $\geq 4,000/\text{mm}^3$  with an absolute neutrophil count  $\geq 1,500/\text{mm}^3$
  - Hemoglobin  $\geq 9$  g/dL
  - Platelet count  $\geq 75,000/\text{mm}^3$

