## **10.0 ASSESSMENT OF EFFICACY**

### **10.1 Evaluation of Disease**

Monitoring for disease status via cystoscopy, cytology, and biopsy if indicated, will be conducted every 3 months during treatment and follow up for 2 years then every 6 months for up to a year per SOC. Disease-free status is defined as no evidence of disease, which in turn is defined as negative cytology, negative cystoscopy, and negative biopsy if clinically indicated.

Recurrence is defined as disease that has recurred to the same extent of disease (i.e. same stage/severity) or to a lower stage/severity of disease compared to screening.

Persistent disease is defined as evidence of CIS disease by 6 months for patients with CIS at screening.

Progression is defined as an increase in T stage from CIS or Ta (at screening) to T1 (lamina propria invasion), development of T2 or greater or lymph node (N+) disease or distant metastasis (M1), or an increase in grade from low to high per the IBCG recommendations.

The stage of disease at the time of recurrence or progression will be captured to distinguish between recurrence to the same extent of disease as at screening (i.e. the same stage/severity) versus recurrence to a lower stage/severity of disease at screening versus persistent disease for CIS versus progression.

The date of confirmation of recurrence or progression is defined as the earliest date on which the diagnosis had been made based on the findings of cystoscopy, urinary cytology, or some other diagnostic imaging technique regardless of whether the patient continues treatment. For the purpose of clarity, in the situation where a patient with CIS documented at screening has evidence of CIS at the 3-month assessment, continues treatment, and still has evidence of CIS at 6 months, that patient will be assumed to have persistent disease from the date of randomization.

For intermediate-risk patients (i.e. without CIS) who have evidence of disease at the 3-month assessment, continue treatment, and still have evidence of disease at 6 months, the date of recurrence would be the date of the 3-month assessment.

If requested, the cystoscopy and cytology reports and images may be appended to the ECRF with all patient identifier information removed and the study site and patient study number written on the report, which is to be signed and dated by the investigator.

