6.5 Prior and Concomitant Medications

Prior and concomitant medications will be coded using World Health Organization (WHO) drug dictionary version March 2013 (or higher), and will be summarised by preferred term and/or ATC class. Medications administered prior to the expected first dose of study will be considered prior medications. Concomitant therapies will be those that are taken on or after Study Day 1 through 30 days after the last dose of study drug. Medications started prior to Study Day 1 and continued into the treatment period will be included in the summary of concomitant therapies. Incidence of prior medication and concomitant therapies will be summarized by preferred term.

7 Efficacy Analyses

All efficacy analyses for recurrence or progression will use standard TNM disease staging, specifically with the following T stage hierarchy: Ta<TIS<T1<T2<T3<T4, and Low Grade<High Grade.

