7.2 Secondary Efficacy Analyses

For time-to-event endpoints (e.g. DFS, OS), Kaplan-Meier / product limit method will be used to estimate the survival distributions over time, and to estimate median time to event. Where appropriate, inference for time-to-event endpoints will be assessed using the Log-rank test statistic, and the treatment effect will be estimated using Cox proportional hazards model. The assumption of proportional hazards will be assessed graphically.

The following will be analysed using Kaplan-Meier time-to-event methodology:

- Time To Recurrence, defined as the time from randomization to recurrence.
 - Recurrence is defined as disease that has recurred to the same extent of disease (ie same stage / severity) or to a lower stage/severity of disease compared to screening.
 - If recurrence has not occurred in a patient, the date of last disease assessment will be used as the timepoint for censoring.
 - The analysis will be repeated in an exploratory manner where recurrence is defined as only those recurrences to the same extent of disease (or greater) as screening.

- Time To Progression, defined as the time from randomization to progression.
 - Progression is defined as an increase in T stage from CIS or Ta (at screening) to T1 (lamina propria invasion), development of T2 or greater or lymph node (N+) disease or distant metastasis (M1), or an increase in grade from low to high per the IBCG recommendations..
 - If progression has not occurred in a patient, the date of last disease assessment will be used as the timepoint for censoring.

- Disease-Free Survival, defined as the time from randomization to recurrence or progression.
 - If a patient has recurred or progressed, then the first date the recurrence or progression has occurred will be used as the timepoint for the event.
 - If a patient has neither recurred nor progressed, then the date of last disease assessment will be used as the timepoint for censoring.

- Overall Survival, defined as the the time from randomization to death.
 - If a patient is still alive, then the patient will be censored on the date of most recent date known alive.
 - If a patient is lost to follow up, then the patient will be censored on the date last known alive.

- Time to cystectomy, defined as the time from randomization to cystectomy.
 - If a patient has not undergone cystectomy, the patient will be censored on the date of last disease assessment.

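### New CIS after high-grade Ta at entry is neither recurrence nor progression under the SAP definitions, so the SAP rules can score it disease free, contrary to protocol 10.1

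*SAP*

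**What the plan says.** The opening of SAP section 7 (printed directly after 6.5) sets one ranking for all recurrence and progression analyses, "with the following T stage hierarchy: Ta<TIS<T1<T2<T3<T4, and Low Grade<High Grade".

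The event categories are these:

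- **Recurrence** (protocol 10.1; SAP 2.1 and 7.2): disease that has "recurred to the same extent of disease (ie same stage / severity) or to a lower stage/severity of disease compared to screening".
- **Progression, stage part** (protocol 10.1; SAP 2.1 and 7.2): "Progression is defined as an increase in T stage from CIS or Ta (at screening) to T1 (lamina propria invasion"), or T2 and above, nodal disease or distant metastasis.
- **Progression, grade part**: "or an increase in grade from low to high per the IBCG recommendations".
- **Persistence** (protocol 10.1 only): "Persistent disease is defined as evidence of CIS disease by 6 months for patients with CIS at screening".

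Eligibility under protocol 4.1 includes "High-risk disease, defined as T1 and/or high-grade and/or CIS", so high-grade Ta without CIS can enter.

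SAP 2.1 and protocol 12.5.1 define one-year DFS as being alive without recurrence or progression. Protocol 10.1 sets a different standard: "Disease-free status is defined as no evidence of disease, which in turn is defined as negative cytology, negative cystoscopy, and negative biopsy" where a biopsy is indicated. Protocol 3.1 and the synopsis state that the analysis of disease-free status follows 10.1.

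**The concern.** The event categories should between them cover every way in which bladder cancer can reappear. Here one does not fit. New CIS in a patient entered with high-grade Ta ranks above the entry stage, so it is not recurrence. It has not reached T1 and involves no low-to-high grade change, so it is not progression. There was no CIS at screening, so it is not persistence.

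At stake is the primary endpoint, where a patient whose bladder cancer has come back could be counted as a success. The time-to-event analyses are also affected, because the same patient would be censored for recurrence, progression and DFS. Two analysts following different parts of the plan could score the same patient in opposite ways.

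**Working it through.** **1. Classification.** The definitions were applied to 30 combinations: 5 entry states (low- and high-grade Ta, CIS, low- and high-grade T1) by 6 later states (the same five, plus T2 or above). CIS was taken as high grade, which the documents do not state. Recurrence required both stage and grade to be the same as or lower than at entry. Exactly one combination was neither recurrence nor progression: high-grade Ta to CIS. Its neighbours are covered:

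| Entry | Later | Category |
|---|---|---|
| Low-grade Ta | CIS | Progression (grade rises) |
| High-grade Ta | CIS | **None** |
| High-grade Ta | High-grade Ta | Recurrence |
| High-grade Ta | T1 | Progression |
| High-grade T1 | CIS | Recurrence (lower stage) |

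If CIS were recorded without a grade, low-grade Ta to CIS would fall into the same gap.

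**2. What the SAP then does with the patient.** SAP 7.1 has three rules.

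- The first makes a patient not disease free for a recurrence, or a dropout, before day 394. New CIS that is not a recurrence does not trigger it.
- The second makes a patient disease free if shown free of disease on day 366 ± 28. CIS still present in that window fails this rule. CIS found earlier and cleared by then passes it, and the protocol lets patients with evidence of disease stay on treatment.
- The third makes a patient disease free if there was no recurrence before day 338 or after day 394. Read literally, this patient passes.

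Under SAP 7.2, a patient with neither event is censored at the last disease assessment.

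**3. The plan's own power figure.** Inputs are 23 evaluable per arm, one-sided alpha 0.10 and 80% power (SAP section 4), Fisher's exact test (SAP 7.1), and 60% versus 90% disease free at one year (protocol 12.6.2). Full binomial enumeration gives power 0.808. The stated 80% is reproduced, and 23 is the smallest number per arm that reaches it.

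**4. Illustration of size.** Let m be the share of all failures that fall in the gap and are scored disease free, equal in every arm. The documents do not give m.

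- Control rate = 0.60 + 0.40m
- Vaccine rate = 0.90 + 0.10m
- Difference = 0.30 × (1 − m)

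| m | Control | Vaccine | Difference | Power, 23 per arm |
|---|---|---|---|---|
| 0 | 60% | 90% | 30 points | 0.808 |
| 5% | 62% | 90.5% | 28.5 points | 0.782 |
| 10% | 64% | 91% | 27 points | 0.754 |
| 20% | 68% | 92% | 24 points | 0.691 |

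For orientation, if 30% to 60% of failures arose in patients with high-grade Ta and 10% to 30% of those appeared as CIS, m would be 0.30 × 0.10 = 3% to 0.60 × 0.30 = 18%. Both shares are assumptions.

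**The case against.** A reader might infer that the plan as a whole scores these patients as disease free. The documents do not support that. Protocol 10.1 requires no evidence of disease, and protocol 3.1 makes 10.1 the standard for the analysis. A patient with CIS fails that standard, and CIS still present in the one-year window also fails the second SAP rule. This part of the objection stands: what remains is a gap in the SAP and a conflict between documents.

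Other arguments are weaker but fair:

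- *SAP 7.1 may use recurrence loosely.* Its rules never mention progression, so a strictly narrow reading would let even a T2 event escape the first rule. That suggests a broader intent, but the intent is not written down.
- *The SAP elsewhere speaks of recurrence to the same extent or greater* (7.1 and the exploratory repeat in 7.2). This too suggests that higher-stage recurrences were meant to count. It also contradicts the main definition, which excludes them.
- *Severity is undefined, and SAP 5.3 lists it apart from stage and grade.* If same or lower stage OR same or lower grade were enough, high-grade Ta to CIS would be recurrence. So would high-grade Ta to high-grade T1, which is progression, although protocol 10.1 records stage in order to tell the two apart. Protocol 12.5.2.1 also explains extent as stage and grade together.
- *Protocol 12.5.2.2 describes progression simply as a greater stage.* Taken alone with the SAP ranking, that would capture Ta to CIS as progression. It does not match the list in protocol 10.1 and SAP 7.2, so it adds a third answer.
- *The size is unknown and may be small.* The 40% of control failures may include deaths, persistent CIS and dropouts. Where CIS appears together with recurrent Ta, the Ta component may already count.

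A reader might also infer a bias in favour of the vaccine. With an equal m in every arm, the difference shrinks, which works against finding an effect. If m differed between arms, the direction could change; the documents give no basis for either.

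**Conclusion.** The point holds as a definitional gap combined with a conflict between the SAP and the protocol. On the natural stage-and-grade reading, with CIS as high grade, new CIS after high-grade Ta belongs to no event category. The DFS definitions in the SAP and protocol 12.5.1 can then make the patient a one-year success, and SAP 7.2 censors the event in time to recurrence, time to progression and DFS. Protocol 10.1 gives the opposite answer on disease-free status. It does not repair the recurrence and progression endpoints, because its own definitions leave the same gap.

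The effect cannot be sized from the documents. The fall in power from 0.808 to between 0.782 and 0.691 depends wholly on an assumed m of 5% to 20%, equal across arms. It shows only that a design sized at the smallest number reaching 80% has little room for missed events. Confidence is high that the texts disagree, and lower on how an analyst would in practice score such a patient.

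**What to change.** In protocol 10.1 and 12.5 and in SAP 2.1, 7.1 and 7.2:

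- Count as recurrence any confirmed bladder cancer found after randomization that does not meet the progression definition, whatever its stage relative to screening, and name new CIS after Ta as an example.
- Keep the separate persistence rule for CIS at screening, and name persistent CIS as a DFS event.
- Leave the IBCG-based progression definition unchanged, and make protocol 12.5.2.1 and 12.5.2.2 refer back to 10.1.
- State in SAP 7.1 that recurrence, progression, persistent CIS or death before the one-year cutoff means not disease free, even if the disease later clears.

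The recurrence wording should not require a documented disease-free status first. The first scheduled on-study cystoscopy in Phase 2 is at Week 13, so new CIS found then may have no such status before it.

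The cost is a few sentences, best settled before unblinding. Protocol 10.1 already has stage recorded at recurrence or progression; that instruction should cover these events too. Observed DFS may be slightly lower.

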7.1 Primary Efficacy Analysis

The primary efficacy parameter is 1 year DFS and will be conducted on the ITT population. It will be calculated as the proportion of patients in the experimental groups and the control who remain disease free at 1 year. Hypothesis testing on the primary endpoint will be done one-sided at a level of significance of $\alpha = 0.10$ using Fisher's exact test. The absolute difference in proportions, as well as the odds ratio, with the associated 95% confidence intervals will also be presented.

The following rules will be used to determine whether a patient is disease free at 1 year or not

- If a patient has a recurrence before day 394 (ie day 366+28 days) or has dropped out of the study before day 394, then the patient is considered to be not disease free at 1 year.
- If a patient is shown to be free from disease on day 366 +/- 28 days, then the patient is considered to be disease free at 1 year.
- If a patient has no recurrence before day 338 (ie day 366-28 days) and after day 394 (day 366+28 days), then the patient is considered to be disease free at 1 year.

If the analysis of the primary endpoint does not suggest any dose response effect between the two vaccine arms, an exploratory analysis will be conducted where the two vaccine arms will be pooled and compared to the control arm for the primary endpoint (proportion of patients alive and disease-free at one year). The outcome will be presented as OR with 95% CI relative to the control group.

In an additional exploratory analysis, the proportion of patients whose disease has recurred to a lower stage than at screening and the proportion of patients whose disease has recurred to the same extent (or greater) as at screening will be compared between the experimental and control groups and presented as an OR with 95% CI.

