#### Phase 2:

In Phase 2, the primary endpoint (proportion of patients alive and disease free at one year) between the two experimental groups and the control will be compared using Fisher's exact test and presented as odds ratios (OR) with 95% confidence intervals (CI) relative to the control group. For the statistical comparisons on the primary endpoint between the two experimental and control groups, there will be no adjustment for multiplicity. ORs will be generated with a simple logistic regression model with one year disease-free survival as the dependent variable and group as the sole independent variable (low dose and high dose vesigenurtacel-L vs. control). If the analysis of the primary endpoint does not suggest any dose response effect between the two vaccine arms, an exploratory analysis will be conducted where the two vaccine arms will be pooled and compared to the control arm for the primary endpoint (proportion of patients alive and disease-free at one year). The outcome will be presented as OR with 95% CI relative to the control group.

Efficacy comparisons between the monotherapy arm and any of the randomized arms will remain exploratory. However, safety and point estimates with appropriate measures of variance (SD, 95% CI) for the efficacy parameters for the fourth arm will be estimated.

The binary secondary endpoints will be presented as OR with appropriate 95% CI.

DFS will also be evaluated as a time to event endpoint, defined as disease recurrence or progression or death from any cause. For time to event endpoints, which will also include OS, time to cystectomy, and burden of repeat TURBT, survival curves will be generated by the method of Kaplan-Meier and compared with the log-rank test. In an exploratory analysis, the weighted log rank test will also be used. The weighted log rank preserves the statistical power that is lost due to the lag time effect in efficacy with immunotherapeutic agents.

Exploratory clinical and laboratory endpoints will be summarized descriptively by time point of collection. Statistical testing and CI will be provided as an aid in reviewing the collected data. A log10 transformation may be used as appropriate in order to determine 95% CI based on a t-test for the log-concentrations, and the bounds will be transformed back to the original scale for presentation purposes. Homogeneity between

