### **12.6.2 Phase 2**

For the randomized portion, a sample size of 75 subjects in the ITT population was selected for this study.

The sample size assessment was based on the following assumptions:

- 75 patients will be randomized to yield 69 evaluable (25 patients per arm)
- A one year disease-free survival rate of 60% in the control and 90% in the respective experimental groups for an absolute difference of 30% in favor of the experimental treatments
- 10% drop-out rate
- Type I error ( $\alpha$ ) = 0.10 and using a one sided test with no adjustment for multiplicity
- Power = 80% to detect a 30% difference in one year disease-free survival between the vesigenurtacel-L groups and the control group
- Patients are followed for three years after the last patient is enrolled

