The objective of the phase 2 study is to compare 1-year disease free survival of two doses of HS-410 + BCG versus BCG + placebo in patients with non-muscle invasive bladder cancer who have undergone TURBT. Given the phase 2 exploratory nature of the study, the overall level of significance will be 0.10, using a one sided test with no adjustment for multiplicity, 75 patients will be randomized in a 1:1:1 (low dose HS-410 plus BCG and high dose HS-410 plus BCG vs. plus BCG + placebo) ratio to yield 69 evaluable (23 patients per arm). 25 patients will be enrolled into the monotherapy arm. Under the assumption that the one-year disease-free survival rate in the control is 60%, the study will have an 80% power to detect a 30% absolute difference between the two experimental groups and the control. Patients will be followed for three years after the last patient has been enrolled and patients will be obtained from approximately 20 participating centers.

5 Statistical Considerations

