5.5 Multiple Testing

The proposed phase 1/2 trial is exploratory, focused on learning and hypothesis generation. Therefore, the preservation of the overall significance level is of lesser importance. However, to address the hazards associated with multiple statistical testing, p-values will only be generated for the primary analysis comparing the two doses of the experimental vaccine to the placebo control. The secondary and exploratory endpoints will be presented as point estimates with associated 95%CI.

6 Summary of Study Data

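### Fisher's test is valid but uses at most 0.0595 of the one-sided 0.10 allowed per comparison; Boschloo's exact test would add about 6.5 to 7.5 points of power once drop-outs count as failures

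*SAP*

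**What the plan says.** - **Test and level.** SAP 7.1, for the ITT population: "Hypothesis testing on the primary endpoint will be done one-sided at a level of significance of" 0.10. It then names the test and the estimates: "using Fisher's exact test. The absolute difference in proportions, as well as the odds ratio, with the associated 95% confidence intervals will also be presented". Protocol 12.1 agrees on the test: "the two experimental groups and the control will be compared using Fisher's exact test".
- **Multiplicity.** SAP section 4: "the overall level of significance will be 0.10, using a one sided test with no adjustment for multiplicity". SAP 5.5 adds that "the preservation of the overall significance level is of lesser importance". Protocol 12.1 and 12.6.2 also decline any adjustment.
- **Sample size.** Protocol 12.6.2 assumes "A one year disease-free survival rate of 60% in the control and 90% in the respective experimental groups". SAP section 4 says "the study will have an 80% power to detect a 30% absolute difference between the two experimental groups and the control", with 75 randomized to give 69 evaluable, 23 per arm. Neither document names the test behind the 80%.
- **Drop-outs.** Protocol 12.6.2 assumes 10%; 69 of 75 evaluable implies 8%. Under SAP 7.1 a patient who leaves before day 394 is not disease-free at one year.

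**The concern.** The sponsor accepts a 10% one-sided false-positive risk for each dose against control. With small arms, a conditional exact test cannot spend all of that, because few outcomes are possible once the total number of successes is fixed. The unused part is power given away, and SAP 5.5 states no aim that the extra strictness would serve.

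This matters more because the ITT rule lowers both analysed success rates and the difference between them. What is at stake is the chance that an effective dose is recognised in a trial with 25 patients per arm. A smaller matter is that the interval reported beside the test is set at a different level from the test.

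**Working it through.** **Inputs.** Success rates 0.60 and 0.90 and drop-out 10% (protocol 12.6.2); 25 randomized and 23 evaluable per arm, one-sided 0.10 (SAP section 4); Fisher's test and the drop-out rule (SAP 7.1).

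**Method.** Let x_C and x_T be the successes among n per arm. Fisher's one-sided p is the hypergeometric probability of x_T or more vaccine successes, given x_C + x_T. Power is the sum of Bin(x_C; n, p_C) × Bin(x_T; n, p_T) over all outcomes with p ≤ 0.10. Size is the same sum with p_C = p_T.

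**1. The plan's own figure.** At 0.60 vs 0.90, Fisher's power is 78.8% at n = 22 and 80.8% at n = 23. The stated 80% is reproduced, and 23 is the smallest n that reaches it. The uncorrected normal formula gives 87.3% at n = 23 and does not reproduce it.

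**2. Size at n = 25.** It is 0.057 at a common rate of 0.60 and 0.059 at 0.54. The maximum over all common rates is 0.0595.

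**3. Boschloo's test at n = 25.** This test uses Fisher's p as its statistic but sets the cut-off so that the maximum size over all common rates is at most 0.10. The cut-off is p ≤ 0.128 and the maximum size is 0.093. For example, 20/25 vs 15/25 has Fisher p = 0.108: not significant by Fisher, significant by Boschloo.

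**4. Power under SAP 7.1.** Assume a drop-out proportion d, equal in both arms, and that drop-outs would otherwise have had their arm's success rate. The analysed rates are then 0.60(1 − d) and 0.90(1 − d).

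| Drop-out, n = 25 | Control vs vaccine | Fisher | Boschloo | Gain (points) |
|---|---|---|---|---|
| None | 60% vs 90% | 84.2% | 86.9% | 2.7 |
| 8% | 55.2% vs 82.8% | 71.8% | 78.3% | 6.5 |
| 10% | 54% vs 81% | 68.9% | 76.4% | 7.5 |

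With Fisher's test unchanged, the drop-out rule alone costs 84.2 − 71.8 = 12.4 points at 8% and 84.2 − 68.9 = 15.3 points at 10%. With Boschloo, the remaining distance to 80% is 80 − 78.3 = 1.7 or 80 − 76.4 = 3.6 points.

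**5. Error over both doses.** The two comparisons share the control arm. Let q(x_C) be the chance that one dose is declared better, given x_C. The chance of at least one false positive is the sum over x_C of Bin(x_C; 25, p) × [1 − (1 − q(x_C))²]. For p from 0.54 to 0.60 this is 0.099 to 0.102 with Fisher and about 0.16 with Boschloo.

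**6. Interval against test.** A two-sided 95% interval leaves 2.5% in each tail; a two-sided 80% interval leaves 10%. Take 21/25 vs 15/25. Fisher's one-sided p is 0.057, so the test rejects. The odds ratio is (21 × 10)/(4 × 15) = 3.5, and the standard error of its logarithm is √(1/21 + 1/4 + 1/15 + 1/10) = 0.68. The Wald 95% interval is 0.92 to 13.3; the lower 80% limit is 1.46.

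**The case against.** The strongest case for leaving the plan alone has four parts.

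- **The level is an upper bound, and Fisher's test respects it.** This stands. Conservatism in small samples is a familiar property, not a mistake.
- **The sample size already allows for it.** This stands too. A reader might infer that Fisher's test leaves the design short of its stated power, or that the plan *loses* about 7 points. The documents do not support that: 80.8% at 23 per arm is what was promised. The 6.5 to 7.5 points are a comparison with a test that was never planned, under an assumed drop-out. Most of the fall below 80% comes from the drop-out rule, which is a separate matter.
- **Boschloo's test weakens error control.** SAP section 4 calls 0.10 the *overall* level, and with Fisher's test the error over both doses is indeed close to 0.10. But the documents do not present that as an aim: they decline any adjustment and, in SAP 5.5, give overall control low priority. The increase has to be disclosed; it does not rule out the change.
- **The 95% interval is descriptive.** This stands. A reader might infer that it turns the primary analysis into a test at one-sided 0.025. SAP 7.1 says only "with the associated 95% confidence intervals will also be presented", and nothing makes the interval a decision rule.

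**Conclusion.** The primary test is not in error. It can be improved cheaply within the level per comparison that the sponsor chose. Boschloo's test adds 6.5 points of power at 8% drop-out and 7.5 at 10%, taking about 72 to 69% up to about 78 to 76%, with no extra patients. Without drop-outs it adds 2.7 points.

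The figures rest on the planned 60% and 90%, exactly 25 per arm, and drop-out that is equal in both arms and unrelated to outcome. Unequal or outcome-related drop-out would change them. A reader might also infer that the new test restores 80% power; under these assumptions it does not.

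**What to change.** - **SAP 7.1 and protocol 12.1, with the synopsis aligned:** replace Fisher's test by Boschloo's exact unconditional test, one-sided at 0.10 for each dose against control. State that size is maximised over the whole range of common success rates and that the cut-off is computed at the arm sizes actually randomized. Settle this before any unblinding, including the optional unblinded Week 25 analysis in protocol 12.1.
- **SAP section 4:** describe 0.10 as the level per comparison, and state that the chance of at least one false positive over both doses is about 0.16.
- **Optional, SAP 7.1:** show a two-sided 80% interval beside the 95% one and say that it corresponds to the level of the test. This changes no test result. An 80% Wald interval need not agree with an exact test in every table, so the test remains the decision rule.

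The cost is wording in both documents, a short validated program, and the rise in two-comparison error from about 0.10 to about 0.16. If the sponsor wants an overall level near 0.10, keeping Fisher's test is defensible; the SAP should then say that this is the reason.
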